13.5 Secondary Analyses

To compare the effect of IV magnesium followed by 12 weeks vs. 24 weeks of oral magnesium, we will calculate the difference between the number of EBV-infected cells (cohort 1) and NKG2D expression in CD8+ T cells (cohort 2) at 12 weeks to 24 weeks in Part II. We will also calculate the difference in NKG2D expression between the 2 cohorts at the same timepoints.

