- Cohort 2: Difference between NKG2D expression in CD8 T cells after 12 weeks of oral magnesium supplementation and after 12 weeks of placebo.

Secondary Endpoints:

- Incidence and severity of adverse events (AEs) throughout the study.
- Contingent upon patient participation in Part II, differences in EBV viral load and number (or percent) of EBV-infected B cells (cohort 1) or NKG2D expression in CD8 T cells (cohort 2) by duration (12 weeks of IV+oral versus 24 weeks of IV+oral) of magnesium supplementation regimen.
- Change in the intracellular pool of free Mg²⁺ by duration of magnesium supplementation regimen.
- evaluate the difference in NKG2D expression between patients with high EBV titers and patients with low or negative titers.

Exploratory Endpoints:

- Change in CD4 T cell counts, B cell counts (or percent), and/or in NKG2D expression on NK (CD3-CD56+) cells.
- Quantification of EBV-infected B cells as determined by flow cytometry and FISH.
- Percent of anemia, neutropenia, thrombocytopenia, and abnormal liver enzymes.
- Difference in number and severity of infections between placebo and magnesium treatment periods.
- Difference in number of health-related days of missed school/work between placebo and magnesium treatment periods.
- Difference in number of emergency room visits and hospital admissions between placebo and magnesium treatment periods.

TABLE OF CONTENTS

Study Staff Roster.....	2
Protocol Summary	3
List of Abbreviations.....	8
Précis.....	10
1 Background Information and Scientific Rationale	11
1.1 Background and Summary of Relevant Pre-clinical Studies.....	11
1.1.1 Rationale	14
2 Study Objectives	16
2.1 Primary Objectives.....	16
2.2 Secondary Objectives	16
2.3 Exploratory Objectives	16
3 Study Design.....	16
3.1 Description of the Study Design	16
3.2 Study Endpoints.....	18
Primary Endpoints	18
Secondary Endpoints	18
Exploratory Endpoints	18
4 Study Population.....	18
4.1 Recruitment Plan	18
4.2 Subject Inclusion Criteria	18
4.3 Subject Exclusion Criteria	19
4.4 Justification for Exclusion of Children <6 years old	19
5 Study Agent/Interventions	19
5.1 Disposition and Dispensation.....	19
5.2 Formulation, Packaging and Labeling	19
5.3 Study Agent Storage and Stability.....	20
5.4 Preparation, Administration, and Dosage of Study Agent/Intervention(s)	20
5.4.1 Description.....	20
5.4.2 Dosing and Administration	20
5.5 Study Product Accountability Procedures	23
5.6 Concomitant Medications and Procedures	23
5.7 Drug Interactions	23

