2.2 Secondary Objectives

- To assess the safety and tolerability of MgSO₄ IV infusion and oral magnesium L-threonate.
- To evaluate the effects of magnesium supplementation on intracellular free Mg²⁺ concentrations in peripheral blood T cell lymphocytes.
- Contingent upon patient participation in Part II, to study the effect of 12 weeks vs. 24 weeks of oral magnesium supplementation after 3 days of IV magnesium on EBV viral load and number (or percent) of EBV-infected B cells (cohort 1) or NKG2D receptor expression on CD8 T cells (cohort 2) in patients with XMEN syndrome.
- To evaluate the difference in NKG2D expression between patients with high EBV titers and patients with low or negative titers.

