3.2 Study Endpoints

Primary Endpoints

- Cohort 1: Difference between the absolute number of EBV-infected B cells (by EBV FISH) after 12 weeks of oral magnesium supplementation and after 12 weeks of placebo.
- Cohort 2: Difference between NKG2D expression in CD8 T cells after 12 weeks of oral magnesium supplementation and after 12 weeks of placebo.

Secondary Endpoints

- Incidence and severity of AEs throughout the study.
- Contingent upon patient participation in Part II, differences in EBV viral load and number (or percent) of EBV-infected B cells (cohort 1) or NKG2D expression in CD8 T cells (cohort 2) by duration (12 weeks of IV+oral versus 24 weeks of IV+oral) of magnesium supplementation regimen.
- Change in the intracellular pool of free Mg²⁺ by duration of magnesium supplementation regimen.
- Change in NKG2D expression in cohorts 1 and 2.

Exploratory Endpoints

- Change in CD4 T cell counts, B cell counts (or percent), and/or in NKG2D expression on NK (CD3-CD56+) cells.
- Quantification of EBV-infected B cells as determined by flow cytometry and FISH.
- Percent of anemia, neutropenia, thrombocytopenia, and abnormal liver enzymes.
- Difference in number and severity of infections between placebo and magnesium treatment periods.
- Difference in number of health-related days of missed school/work between placebo and magnesium treatment periods.
- Difference in number of emergency room visits and hospital admissions between placebo and magnesium treatment periods.

4 Study Population

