6.3 Part I: Oral study agent (Week 1 to Week 24)

Oral magnesium or placebo (Week 1 to Week 12)

On Day 0, patients will begin to self-administer the oral study agent according to the dose escalation scheme in section 5.4.2.

Dose escalation every 2 weeks (Weeks 2, 4, and 6, or until maximum tolerated dose is reached)

Prior to increasing the study drug dose the study staff will contact patients to review their medication administration, assess for AEs and approve escalation to the next dose. In addition, patients will be contacted 1 week after dose escalation to assess for AEs.

4-week follow-ups (Weeks 4 and 8 +/- 1 week)

Patients will come to NIH for clinical and research evaluations to include:

- Medical history and physical exam

Clinical laboratory evaluations:

- CBC with differential
- Acute care panel, mineral panel, hepatic panel
- EBV by PCR
- CMV by PCR
- CRP
- ESR
- Total and ionized serum magnesium
- TBNK
- Spot urine magnesium

Research assays:

- Intracellular free Mg²⁺
- EBV FISH
- RNA extraction
- NKG2D expression on CD8 T cells and NK cells by flow cytometry
- Storage of serum, plasma, and PBMCs

Week 12 (+/- 1 week)

At the conclusion of 12 weeks of study agent patients will return to NIH for the following evaluations:

- Medical history and physical exam
- EKG

Clinical laboratory evaluations:

- 24-hour urine collection for magnesium
- CBC with differential
- Acute care, mineral and hepatic panels
- Quantitative immunoglobins
- Lymphocyte phenotyping
- CMV by PCR
- EBV by PCR
- ESR
- CRP
- Total and ionized serum magnesium

Research assays:

- Intracellular free Mg²⁺
- EBV FISH
- RNA extraction
- NKG2D expression on CD8 T cells and NK cells by flow cytometry
- Storage of serum, plasma, and PBMCs

Crossover (Week 13-24 +/- 1 week)

To crossover (from magnesium supplementation to placebo or from placebo to magnesium supplementation), patients will return any unused study agent and begin dose escalation with a new oral agent (magnesium or placebo). Patients will be provided dosing instructions and a medication log for recording AEs (Appendix C).

Dose escalation every 2 weeks (2, 4, and 6 weeks after the start of crossover, or until maximum tolerated dose is reached)

Prior to increasing the study drug dose staff will contact patients to review their medication administration, assess for AEs and approve escalation to the next dose. In addition, patients will be contacted 1 week after dose escalation to assess for AEs.

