Follow-up visits:

Patient will come to NIH at Weeks 16 and 20 for the same clinical and research evaluations as Weeks 4 and 8.

Week 24 (+/- 1 week)

At the end of 24 weeks, patients will repeat all the evaluations that were performed at the end of Week 12. This will be the last visit for patients who do not continue to Part II. Part II will be conducted only among patients in whom oral magnesium is not more effective than placebo.

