13.2 Statistical Analysis

Cohort 1

The primary analysis will compare the difference between the number of EBV-infected B cells at the end of the treatment and control periods. Specifically, for each patient, the number of EBV-infected B cells at the end of the placebo period will be subtracted from the number of EBV-infected B cells at the end of the treatment period. The mean of these differences in all patients will be calculated and these values will be used to form the test statistic for a paired t-test. If magnesium treatment does not work, the true mean difference will be 0. If magnesium lowers the number of EBV-infected B cells, the true mean difference will be less than 0.

To determine which participants will continue to Part II, we will evaluate the number of EBV infected B cells (by EBV FISH) in each patient after 12 weeks of oral magnesium and after 12 week of placebo. If a patient has a 3.16-fold or 68.35% reduction with oral magnesium as compared with placebo, then that patient's study participation will end. Those patients who do

not meet this outcome will proceed to Part II (IV magnesium). Participation in Part II will depend on the result for each individual patient. We have chosen a 3.16-fold (68.35%) reduction as this is equivalent to a 0.5 log decrease.

Contingent upon patient participation in Part II, secondary analysis will compare the numbers of EBV-infected B cells at the end of 12 weeks versus 24 weeks of oral supplementation.

Cohort 2

The primary analysis will compare the difference between the mean fluorescence intensity (MFI) of NKG2D on CD8+ T cells at the end of the treatment and control periods. Specifically, for each patient, the MFI for NKG2D at the end of the placebo period will be subtracted from the MFI for NKG2D at the end of the treatment period. The mean of these differences in all patients will be calculated and these values will be used to form the test statistic for a paired *t*-test. If magnesium treatment does not work, the true mean difference will be 0. If magnesium increased the surface expression for NKG2D on CD8+ T cells, the true mean difference will be less than 0.

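### The NKG2D comparison of high- and low/no-EBV patients is not tied to Part II, but its only written analysis is at Part II timepoints, so it omits every Part I responder and compares subsets selected by different rules

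*Combined protocol and SAP*

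**What the plan says.** Section 2.2 lists the objective without a timepoint or a condition: "To evaluate the difference in NKG2D expression between patients with high EBV titers and patients with low or negative titers". The objective just before it, on duration of supplementation, does open with a condition on Part II participation.

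The matching endpoint is worded in two ways. The Protocol Summary has a between-group difference: "evaluate the difference in NKG2D expression between patients with high EBV titers and patients with low or negative titers". Section 3.2 has "Change in NKG2D expression in cohorts 1 and 2". Neither is tied to Part II, although a neighbouring endpoint in each list is.

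Section 13.5 first sets out the duration comparison, "at 12 weeks to 24 weeks in Part II", and then adds "We will also calculate the difference in NKG2D expression between the 2 cohorts at the same timepoints". Section 13 contains no other cross-cohort NKG2D analysis.

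On who reaches Part II, section 6.3 says of week 24: "This will be the last visit for patients who do not continue to Part II". Section 13.2 ends participation in cohort 1 on EBV-infected B cells ("If a patient has a 3.16-fold or 68.35% reduction with oral magnesium as compared with placebo"), and in cohort 2 on a rise of at least 2-fold in NKG2D on CD8 T cells.

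On data, section 6.3 lists "NKG2D expression on CD8 T cells and NK cells by flow cytometry" at weeks 4, 8 and 12 and repeats it at weeks 16, 20 and 24, with no cohort restriction. Appendix B agrees.

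**The concern.** The objective is about high- and low/no-EBV patients as enrolled. An analyst who follows 13.5 would answer it only in patients for whom oral magnesium had not met the response criterion.

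The two remaining groups are also not comparable subsets. Cohort 2 is cut on the variable being compared: patients with large NKG2D rises are gone. Cohort 1 is cut on a different variable, so its patients with large NKG2D rises leave only to the extent that NKG2D and EBV responses go together. A cohort difference in Part II could therefore come from the entry rules, or a real one could be hidden by them.

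At stake is the answer to one secondary objective. The primary analyses and the decision on who enters Part II do not depend on it.

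**Working it through.** **Is there a figure to reproduce?** The plan gives none for this comparison. Its only power figure, 90% at 1.15 SD with 10 patients (13.3), is for the within-patient primary test. It reproduces at 0.898 with the noncentral t distribution (9 degrees of freedom, noncentrality 1.15 × √10), but does not bear on the cross-cohort contrast.

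**Step 1: the text.**
- Objective and endpoints (2.2, Protocol Summary, 3.2): no Part II condition, while neighbouring items have one.
- Analysis (13.5): Part II timepoints only.
- Patients with Part II data (6.3, 13.2): Part I non-responders only.
- NKG2D in Part I (6.3, Appendix B): scheduled for every patient.

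The omission of responders follows from the text and needs no assumption beyond at least one patient responding.

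**Step 2: loss of precision.** Inputs: 10 patients per cohort (Protocol Summary); an assumed Part I response rate, equal in both cohorts, because the plan gives none; a common SD that is the same in the reduced set.

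95% CI half-width in SD units = t(0.975; n1 + n2 − 2) × √(1/n1 + 1/n2)

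| Assumed response rate | Patients compared | Calculation | Half-width |
|---|---|---|---|
| none lost | 10 v 10 | 2.101 × √(2/10) | 0.94 SD |
| 10% | 9 v 9 | 2.120 × √(2/9) | 1.00 SD |
| 30% | 7 v 7 | 2.179 × √(2/7) | 1.16 SD |
| 50% | 5 v 5 | 2.306 × √(2/5) | 1.46 SD |
| 70% | 3 v 3 | 2.776 × √(2/3) | 2.27 SD |

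**Step 3: can the entry rules alone produce a difference?** Take two cohorts with identical NKG2D behaviour. On the log2 scale let mean response be μ, its SD s, and the correlation between EBV and NKG2D responses ρ. Assume perfect measurement and full persistence of the response into Part II. A 2-fold rise is 1 on this scale, so c = (1 − μ)/s, and Φ(z) is the share of cohort 1 entering Part II. The expected difference, cohort 2 minus cohort 1, is

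d = −s × φ(c)/Φ(c) + ρ × s × φ(z)/Φ(z)

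- μ = 0, s = 0.5, ρ = 0: c = 2; d = −0.5 × 0.0540/0.9772 = −0.028, and 2^d − 1 is about −2%.
- μ = 1.5, s = 0.8, ρ = 0: c = −0.625; d = −0.8 × 0.328/0.266 = −0.987, about −50%.
- μ = 0, s = 0.8, ρ = 0.7, half of cohort 1 entering: c = 1.25, z = 0; d = −0.8 × 0.1826/0.8944 + 0.7 × 0.8 × 0.3989/0.5 = −0.163 + 0.447 = +0.28, about +22%.
- No variation in true response: d = 0.

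Every input in this step is assumed. The cases show that a spurious difference is possible and that it can go either way. They do not estimate it.

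**The case against.** The strongest reply is that this is a minor gap. Section 13.5 promises only to calculate a difference, attaches no test to it, and nothing forbids a Part I comparison. The data are collected in any case, so an analysis could be added without changing any visit. All of that stands and limits the severity. It does not remove the point: the timepoints that are written answer the objective in the wrong set of patients.

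It can also be said that the same timepoints means 12 and 24 weeks in general, hence Part I as well. The only antecedent in 13.5 is Part II. If Part I was meant, the text has to say so.

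Three stronger readings are tempting, and the documents do not support them.
- A reader might infer that the Part II contrast is known to be biased, with cohort 2 looking falsely low. Response rate, spread, persistence and the EBV–NKG2D correlation are not given. Section 13.1 expects better NKG2D to go with fewer EBV-infected B cells, which would offset some or all of the selection effect or even reverse its sign.
- A reader might infer that no Part I analysis of NKG2D exists for cohort 1. Section 13.2 gives none, but 13.4 describes a paired test of EBV-infected B cells or NKG2D without naming cohorts. The likelier reading is one endpoint per cohort, but the absence is not absolute.
- A reader might infer that the 3.2 endpoint is itself a between-cohort contrast left unanalysed. Its wording names change in the two cohorts and no contrast. The contrast comes from 2.2 and the Protocol Summary.

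**Conclusion.** The point holds. The objective has no Part II condition, its only cross-cohort analysis is confined to Part II, and that analysis drops all Part I responders and compares non-responders chosen by two different criteria. This rests on the text alone.

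The size depends on response rates that the plan does not state. At an assumed 30% or 50% in each cohort, the comparison falls from 20 patients to 14 or 10, and the interval half-width rises from 0.94 SD to 1.16 or 1.46 SD. Selection bias is a real possibility, but neither its size nor its direction can be established from the documents.

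It should be corrected, as a secondary matter. The comparison carries no test, and the primary analyses are untouched.

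**What to change.** Replace the last sentence of 13.5 with text to this effect:

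*The difference between cohorts 1 and 2 in NKG2D MFI on CD8 T cells will be estimated with 95% confidence intervals in all randomized patients with the relevant Part I measurements. The main contrast is the within-patient change, end of magnesium minus end of placebo (weeks 12 and 24), also shown by arm. Levels at the end of each period are supportive. The cohort difference at 12 and 24 weeks of Part II is descriptive and applies to Part I non-responders only.*

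Two further edits belong with it.
- Add a pre-treatment baseline comparison, which is free of treatment and of response selection. Baseline NKG2D sampling must first be reconciled: 3.1 describes three-day draws without a cohort split, 6.2 makes the baseline assay depend on cohort and reserves the three-day NKG2D draw for cohort 2, and Appendix B marks baseline NKG2D with no cohort restriction.
- Reconcile the endpoint wording in the Protocol Summary (difference) with 3.2 (change).

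The cost is a few sentences. The week 12 and 24 assays are already scheduled for everyone; the baseline comparison needs the sampling text settled. The limits should be stated. Part I has no washout between periods, so placebo values in Arm 1 may carry some magnesium effect. A different arm split in the two cohorts would let a period effect into the main contrast, which is why it should also be shown by arm. Patients who leave early have no change value, though they can contribute to the levels for a period they completed. Precision is low even with 10 versus 10.

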13.6 Randomization within each cohort

Patients will be allocated to Arm 1 or Arm 2 using a permuted block design with block size of 20. This means that exactly 10 patients will be randomly assigned to each arm. The study statistician will provide the randomized list of arm assignments.

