A Double-blind, Placebo-controlled, Crossover Study of Magnesium Supplementation in Patients with XMEN Syndrome

NIAID Protocol Number: 15-I-0161

Sponsored by: NIAID

Version Number: 9.0

Date: March 8, 2019

Principal Investigator: [name]

Study Staff Roster

Principal Investigator:

[name] Laboratory of Immunology (LI)/NIAID

Associate Investigators:

[name] LI/NIAID

[name] Laboratory of Host Defenses/NIAID

[name] LI/NIAID

[name], ScM, CGC LI/NIAID

[name] National Heart Lung and Blood Institute/
Cardiovascular and Pulmonary Branch

[name] Biostatistics Research Branch/NIAID

Study Coordinator:

[name] LCID/NIAID

Medical Advisory Investigator:

[name] LID/NIAID

Protocol Summary

Full Title:	A double-blind, placebo-controlled, crossover study of magnesium supplementation in patients with XMEN syndrome
Short Title:	XMEN syndrome and magnesium
Clinical Phase:	Phase 1 and 2
Conducted by:	NIAID/LI
Principal Investigator:	[name]
Sample Size:	n=20 (n=10 for each cohort)
Accrual Ceiling:	n=30
Study Population:	Patients \geq 6 years with X-linked immunodeficiency with magnesium defect and increased susceptibility to Epstein-Barr virus (EBV) infection and neoplasia (XMEN) syndrome. Subjects will be divided into 2 cohorts: Cohort 1 (high EBV): Subjects with baseline blood EBV viral load \geq 5,000 copies/mL or EBV log \geq 3.7 IU/mL. Cohort 2 (low/no EBV): Subjects with baseline blood EBV viral load <5,000 copies/mL or EBV log <3.7 IU/mL.
Accrual Period:	4 years
Study Design:	A randomized, double-blind, placebo-controlled, crossover study to evaluate the safety and efficacy of oral magnesium L-threonate in subjects with XMEN syndrome. In Part I, patients within each cohort will be randomized into 2 arms. Each arm will receive 12 weeks of either oral magnesium L-threonate or placebo followed by crossover treatment for another 12 weeks. Patients in cohort 1 who experience \geq 0.5-log reduction in the number of EBV-infected B cells and patients in cohort 2 who experience \geq 2-fold increase in NKG2D receptor expression on CD8 T cells during oral magnesium treatment as compared to placebo will have completed the study. Patients who do not meet these respective criteria will undergo a 2-week washout and transition to Part II in which they will be hospitalized to receive 3 days of IV MgSO ₄ . These patients will then restart escalating doses of oral magnesium and continue for 24 weeks, at which point participation will be complete.

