3.1 Description of the Study Design

Patients enrolled onto the study will be divided into 2 cohorts. Patients in cohort 1 (high EBV group) will have baseline blood EBV viral load \geq 5,000 copies/mL or EBV log \geq 3.7 IU/mL. Patients in cohort 2 (low/no EBV group) will have baseline blood EBV viral load $<$ 5,000

copies/mL or EBV log <3.7 IU/mL. The study will be conducted in 2 parts; for each patient, participation in Part II is contingent upon the outcome of Part I. Part I is a randomized, double-blind, placebo-controlled, crossover study to evaluate the efficacy of oral magnesium L-threonate compared to placebo. Following an initial washout of magnesium-containing supplements, patients within each cohort will be randomized into 2 arms (**Figure 5**). Arm 1 will receive 12 weeks of magnesium supplementation followed by 12 weeks of placebo. Arm 2 will receive 12 weeks of placebo followed by 12 weeks of magnesium supplementation. Magnesium supplementation will consist of escalating doses of daily, orally self-administered magnesium L-threonate.

After 24 weeks of study, patients who show a 0.5-log (3.16-fold or 68.35%) reduction in the number of EBV-infected B cells (cohort 1) or or a ≥ 2 -fold increase in NKG2D receptor expression on CD8 T cells (cohort 2) during oral magnesium treatment as compared to placebo will end study participation. Such patients may remain on oral magnesium after completion of the study under the supervision of a primary care physician. Patients in whom oral magnesium was not clearly effective will begin a 2-week washout and proceed to Part II. Such patients will be hospitalized to receive 3 days of IV MgSO₄ administered 3 times per day for a total daily dose of 30/mg/kg/day. Then they will restart escalating doses of orally self-administered magnesium L-threonate and continue for the remaining 24 weeks of the study.

Prior to magnesium supplementation, blood draws on 3 consecutive days will be used to establish baseline NKG2D expression on CD8+ T cells, numbers of EBV-infected B cells, EBV viral load and intrasubject variability. The number of EBV-infected B cells and other relevant measures will be recorded before and after each supplementation period. The investigator measuring NKG2D expression and the numbers of EBV-infected B cells by FISH (primary outcome measures) will be blinded to the treatment group.

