10.9 Replacement for Withdrawn Subjects

Withdrawn subjects may be replaced if eligible replacements can be identified.

11 Remuneration Plan

Eligible subjects will be compensated for travel according to the NIAID/NIH travel policy. Subjects will receive financial compensation for the time and inconvenience of study participation according to the NIH CC volunteer guidelines at \$10 per inconvenience unit (IU). Total compensation will be \$720 (completion of Part I only) or \$1365 (completion of Part I and Part II). See Appendix D for detailed compensation amounts. Subjects will be compensated at the completion of part I, part II, or at time of withdrawal from the study (for portion of study completed).

12 Clinical Monitoring Structure

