13.3 Sample Size Justification

For cohort 1, the primary endpoint is the difference between the absolute number of EBV-infected B cells (EBV FISH) after 12 weeks of magnesium supplementation and after 12 weeks of placebo. With 10 subjects, there is 90% power to detect 1.15 standard deviation change by the 2-sided paired *t*-test with type I error rate of 0.05. To evaluate EBV change over time, we will compare the absolute number of EBV-infected B cells at the end of the control period and at the end of the treatment period. We will report the mean change in EBV with 95% confidence intervals.

For cohort 2, the primary endpoint is the difference between the MFI for NKG2D surface expression on CD8+T cells after 12 weeks of magnesium supplementation and after 12 weeks of placebo. With 10 subjects, there is 90% power to detect 1.15 standard deviation change by the 2-sided paired *t*-test with type I error rate of 0.05. To evaluate NKG2D change over time, we will compare the MFI for NKG2D surface expression on CD8+ T cells at the end of the control period and at the end of the treatment period. We will report the mean change in NKG2D with 95% confidence intervals.

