13.4 Power calculation

Table 3 gives the detectable difference (EBV-infected B cells at end of magnesium – EBV-infected B cells or NKG2D surface expression at end of placebo) with various sample sizes. The differences shown in the table are functions of the standard deviation. For example, with 10 patients if the standard deviation of the differences is 1 there is 90% power to detect a true difference of 1.15. If the standard deviation is 2, there is 90% power to detect a difference of $2.3=1.15*2$. The values in the table are based on using a t-test for the analysis. **Table 3** gives the ratio of the difference to the standard deviation that can be detected with various sample sizes in each group to obtain 90% power. At the end of the study a paired *t*-test will be used to determine whether the difference in the number of EBV-infected B cells or NKG2D expression in CD8+ T cells between the period treated with magnesium and treated with placebo (number of EBV-infected B cells or MFI for NKG2D expression after 3 months of magnesium treatment – number of EBV-infected B cells or MFI for NKG2D expression after 3 months of placebo treatment) is different from 0.

Table 3. Detectable differences with various sample sizes with 90% power and 2-sided type I error rates of 0.05. The differences are shown as functions of the standard deviations

Total sample size (with half of subjects randomized to each sequence)	Difference/standard deviation
10	1.15
12	1.03
14	0.94
16	0.87
18	0.81
20	0.76

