13.7.2 Unblinding

13.7.2.1 Scheduled Unblinding

Unblinding will occur for every participant at the end of the 24-week period in Part I after the laboratory analysis for the primary endpoints (NKG2D and EBV by FISH) has been completed. At this point, participants will be informed about their treatment assignment in Part I.

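### A block of 20 with ten patients per arm does not fit cohorts of 10, so the sequence split in each cohort is left to chance under a primary test with no period term

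*Combined protocol and SAP*

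**What the plan says.** The Protocol Summary gives the sample size as "n=20 (n=10 for each cohort") and an accrual ceiling of 30. Section 3.1 states that "patients within each cohort will be randomized into 2 arms": magnesium then placebo, or placebo then magnesium. Section 13.6, whose heading also places the randomization within cohorts, describes allocation "using a permuted block design with block size of 20. This means that exactly 10 patients will be randomly assigned to each arm".

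Section 13.2 sets a separate primary paired t-test for each cohort. Each patient's end-of-placebo value is subtracted from the end-of-magnesium value, and "The mean of these differences in all patients will be calculated and these values will be used to form the test statistic". Sections 13.2 to 13.5 contain no period or sequence term. Section 13.3 adds, for cohort 1, "We will report the mean change in EBV with 95% confidence intervals", with the same for NKG2D in cohort 2. Table 3 in Section 13.4 lists 10 patients with a detectable difference of 1.15 SD, under a column headed "Total sample size (with half of subjects randomized to each sequence").

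Two other provisions matter. Section 10.9 says "Withdrawn subjects may be replaced if eligible replacements can be identified". Section 13.7.2.1 says "Unblinding will occur for every participant at the end of the 24-week period in Part I after the laboratory analysis" for the primary endpoints, and Section 13.7.2.2 unblinds anyone who does not complete the 24 weeks.

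**The concern.** No single list satisfies all of these statements. Ten per arm in each cohort would need 2 × 20 = 40 patients, which exceeds the ceiling of 30. If each cohort has its own block of 20, a cohort of 10 uses only half of it, and nothing forces that half to be balanced. If both cohorts share one block of 20, ten per arm is right for the whole trial, but the list does not control the split inside a cohort.

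Sequence is randomized in a crossover so that a change between periods does not pass for a treatment effect. The planned test pools patients over sequence, so only an equal split removes a period shift from the estimate. At stake is whether each cohort's reported mean change and confidence interval carry part of any such shift.

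**Working it through.** **Inputs.** From the documents: 10 per cohort, block of 20 (10:10), two-sided alpha 0.05, paired t-test, 1.15 SD detectable with 90% power. Assumed, because the documents give no period effect: a shift π (period 2 minus period 1) of 0.25, 0.5 or 1.0 SD of the within-patient difference within a sequence.

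**The plan's own figure.** Power of the paired t-test comes from the noncentral t with df = 9 and noncentrality 1.15 × √10. This gives 89.8%; exactly 90% needs 1.155 SD. The other rows of Table 3 reproduce as 1.029, 0.938, 0.868, 0.811 and 0.764. With no period effect these figures do not depend on the split.

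**Split in a full cohort of 10.** P(k in Arm 1) = C(10,k)² / C(20,10), with C(20,10) = 184,756. For 5:5 this is 252² / 184,756 = 34.4%. For 6:4 in either direction it is 2 × 210² / 184,756 = 47.7%. The formula is the same for a separate list and for a shared list on which each cohort takes 10 slots. With a shared list and cohorts of 8 and 12, an equal split has probability 35.0%; with 6 and 14, 37.1%. With two separate lists, both cohorts are 5:5 with probability 0.344² = 11.8%.

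**Bias given the split.** The magnesium-minus-placebo difference has mean δ − π in Arm 1 and δ + π in Arm 2. The pooled mean is therefore δ + π(n₂ − n₁)/10.

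**Type I error of the paired t-test** (simulated, 300,000 to 400,000 runs per case):

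| Split | Probability | Share of π in the estimate | π = 0.25 | π = 0.5 | π = 1.0 |
|---|---|---|---|---|---|
| 5:5 | 34.4% | 0 | 4.4% | 3.0% | 0.7% |
| 6:4 | 47.7% | 20% | 4.6% | 3.7% | 1.6% |
| 7:3 | 15.6% | 40% | 5.4% | 6.0% | 6.3% |
| 8:2 | 2.2% | 60% | 6.6% | 10.5% | 20.0% |
| 9:1 | 0.1% | 80% | 8.4% | 18.1% | 47.5% |
| Average | | 0 | 4.7% | 4.0% | 2.5% |

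At 7:3 the bias is 0.10, 0.20 or 0.40 SD. The test's own standard error also contains the period variance, and is about √[(1 + π² × 4 × 7 × 3/90)/10]. Relative to that, the bias is 0.31, 0.57 or 0.91 standard errors.

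**Power at 1.15 SD.** With the paired test at 5:5 it is 88.4%, 84.0% and 63.7% for the three shifts. Averaged over block-of-20 splits it is 88.2%, 83.1% and 62.7%. The block therefore accounts for about 0.2 to 1 point, and the rest of the loss comes from the missing period term. Given 7:3 and π = 0.5, power is about 69% or 94%, depending on which sequence is larger.

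**Period-adjusted comparison.** This is a two-sample t-test of period differences by sequence, with df = 8 and noncentrality 1.15 / √[(1/n₁ + 1/n₂)/4]. Power is 88.8% at 5:5, 87.6% at 6:4 and 83.0% at 7:3, whatever the shift. The detectable effect at 5:5 is 1.17 SD.

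**The case against.** The strongest reply is that the harm is small and hypothetical. No period effect is documented. The bias averages to zero over randomizations. At 5:5 and 6:4, which together cover 82% of full cohorts, type I error stays below 5%, and the large error rates belong to splits with about 2% probability. All of this stands and limits the weight of the point. It does not remove the bias in the one split that each cohort will actually have.

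Second, the SD in Table 3 is the SD of the differences, which can be read as already including the period component. On that reading, averaged power is 90.0% to 92.1% for the three shifts and the stated 90% holds. This stands too, so the point does not rest on lost power.

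Third, ten per arm is correct for the planned total of 20, and the actual list is not in the documents. That is so, but the section describes randomization within cohorts, and no reading of it secures balance there.

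Fourth, a larger block is harder to predict, which matters when patients are unblinded one by one. With all earlier assignments known, the best guess is right for 6.5 of 10 patients with a block of 10, against 5.5 with a block of 20. This is a real cost of the fix.

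Fifth, timing: the start date is 6/1/2015, accrual was planned for 4 years, and this version is dated March 8, 2019. Actual enrolment is not stated, and few slots may remain. The list change may then affect few patients, but the period-adjusted analysis is useful whatever split occurred.

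**Conclusion.** The concern holds. Section 13.6 contradicts the cohort size, and as written it leaves the sequence split in each analysed cohort to chance: unequal in 65.6% of full cohorts and 7:3 or worse in 17.9%. The consequence is a conditional bias in the reported mean change and its interval, equal to 20% of any period shift at 6:4 and 40% at 7:3. In SD units this depends on assumed shifts, since the documents supply none; with no period effect there is no bias. Overall type I error is not inflated, Table 3 is arithmetically correct, and most of the power lost to a period effect comes from the missing period term in Section 13.2 rather than from the block. This should be fixed, but it does not invalidate the design. Carryover is a separate matter and is not assessed here.

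**What to change.** **Section 13.6.** State a separate list for each cohort. Where no one in a cohort has been assigned, use one block of 10 and replace ten per arm with 5 per arm in a full cohort. Where a cohort is partly filled, use one balanced block as long as the remaining slots. With 4 already assigned, this gives 5:5 with probability C(10,2)²/C(20,4) = 2,025/4,845 = 41.8%, against 31.9% with a truncated block of 10 and 34.4% if the block of 20 continues. A list built to complete 5:5 exactly is also feasible at that point, but it is more predictable: after a 4:0 start, five of the six remaining slots would go to one arm. Record which list was used for patients already assigned.

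State how replacements draw from the list, for example from the next slot of a reserve block of 10. Giving a replacement the withdrawn patient's sequence would reveal that assignment, because withdrawals are unblinded. State also that 5:5 is not guaranteed among completers. With a reserve block of 10, completers are 5:5 in 50% to 55% of cases after one replacement and 41% to 44% after two.

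**Sections 13.2 and 13.4.** Add the period-adjusted comparison for each cohort (df = 8, detectable effect 1.17 SD at 5:5). Make it primary only if it is specified before outcomes are known by assignment. Patients are unblinded individually after week 24 and the documents do not say how many have been, so otherwise add it as a sensitivity analysis with the date of the change recorded.

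**Cost.** Wording in three sections and a list for unassigned slots; no extra patients. With no period effect, the adjusted test has 88.8% power against 89.8% at 5:5, or 86.9% against 89.8% on average if the block of 20 is kept. It is the more powerful test only above a shift of about 0.2 SD at 5:5, or about 0.33 SD with the block of 20.
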